11.5.1.1 Stopping Probabilities Under Various Hypothetical References

The study design allows early stopping for futility probabilities under various hypothetical “harm” or “equal” scenarios; examples are included below using EAST 6 (Version 6.5) (number of simulations=10,000, seed=6547):

- “harm” scenario 1: If the true rivaroxaban rate of progression is 35% and the true control rate is 30%, the probability of stopping early for futility is 50.2% at the interim analysis.
- “harm” scenario 2: If the true rivaroxaban rate of progression is 19.5% and the true control rate is 15%, the probability of stopping early for futility is 51.6% at the interim analysis.
- “equal” scenario 1: If the true rivaroxaban rate of progression is 30% and the true control rate is 30%, the probability of stopping early for futility is 25.5% at the interim analysis.
- “equal” scenario 2: If the true rivaroxaban rate of progression is 15% and the true control rate is 15%, the probability of stopping early for futility is 23.0% at the interim analysis.

12 SAFETY AND TOLERABILITY

Safety analyses will be conducted in the safety population. Safety outcomes will include:

- Grade 3 AEs
- Grade 4 AEs
- AEs resulting in study intervention discontinuation
- SAEs
- AESIs (including major bleeding and severe hypersensitivity to rivaroxaban)

12.1 Adverse Events

AEs will be coded using MedDRA version 22.1 or higher. AE severity will be graded as Grade 1 (Mild), Grade 2 (Moderate), Grade 3 (Severe), Grade 4 (Potentially Life-threatening), or Grade 5 (Death) as referencing to the specific toxicity grading by Division of Acquired Immunodeficiency Syndrome (DAIDS) AE Grading Table [[DAIDS 2017](#)].

AEs starting on or after first day of study intervention will be considered as treatment-emergent. Only AEs within the reporting window will be included within the relevant category in summary tables. All AEs will be listed, regardless of if it was reported within the applicable reporting window.

An AE overview table containing the frequency and percent of participants in each of the following categories (summarized by intervention group) and also the 95% CI (calculated for a single proportion using the Mid-p method):

- Any AE
- Related AEs
- Grade 3 AEs
- Grade 4 AEs
- AEs resulting in study intervention discontinuation
- SAEs
- AEs with outcome of death
- AESIs (including major bleeding and severe hypersensitivity to rivaroxaban)

Additionally, the following will be summarized by SOC and PT for each intervention group:

- Incidence of AEs
- Incidence of related AEs

- Incidence of Grade 3 AEs
- Incidence of Grade 4 AEs
- Incidence of AEs resulting in study intervention discontinuation
- Incidence of SAEs
- Incidence of AEs with outcome of death
- Incidence of AESIs

Summaries of SOC and PT will be sorted alphabetically by SOC and by decreasing frequency of PT in the intervention group. If a participant has more than 1 AE at a given level (e.g., SOC and PT), the participant will only be counted once within that level.

Missing severities and relationship will not be regarded as ‘worst case’.

Incidences of Grade 3 AEs, Grade 4 AEs, and AEs resulting in study intervention discontinuation will be summarized by subgroups.

- Race (white, black, other)
- Ethnicity (Hispanic or Latino, Not Hispanic or Latino)
- Sex (male, female)
- Number of days since onset of symptoms at time of randomization (<6 days or ≥6 days)
- Presence of comorbidities/risks
 - Age (<65 years, ≥65 years)
 - Presence of chronic pulmonary disease, COPD, pulmonary hypertension (Yes, No)
 - Diabetes mellitus (type 1 or type 2) requiring medication or insulin (Yes, No)
 - Hypertension, requiring at least 1 oral medication for intervention (Yes, No)
 - Immunocompromised status due to disease or medication (Yes, No)
 - Chronic disease associated with high risk for severe COVID-19 (Yes, No)
 - BMI groups (<35 kg/m², ≥35 kg/m²)

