**Table 3: Objectives and Endpoints**

Objectives	Endpoints
Primary	
To characterize safety of study intervention	
Through Day 35
 
 
• Frequencies of grade 3 AEs and grade 4 AEs
 
• AEs resulting in study intervention discontinuation
 
• All SAEs
 

To assess efficacy of study intervention	
 
• Proportion of participants who progress to moderate or severe disease category or higher (Gates MRI ordinal scale <math>\geq 3</math>) through Day 28
 

Secondary	
To assess clinical efficacy of study intervention	
 
• Time to disease resolution, defined as BOTH viral clearance (two consecutive negative diagnostic tests) and symptoms resolution (new onset COVID-19 symptoms resolved, and pre-existing symptoms returned to baseline*) through Day 28
 
• Time to disease resolution, defined as symptoms resolution only (new onset COVID-19 symptoms resolved, and pre-existing symptoms returned to baseline*) through Day 28
 
• Proportion of participants who progress to moderate or severe disease category or higher (Gates MRI ordinal scale <math>\geq 3</math>) at Days 8, 14 and 21
 
• Proportion of participants who achieve disease resolution at Days 8, 14, 21 and 28
 
• Gates MRI scale score at Days 8, 14, 21 and 28
 
• WHO ordinal scale score at Days 8, 14, 21 and 28
 
• Incidence and number of days of hospitalization at Days 8, 14, 21 and 28
 

Exploratory objectives	
To assess virological efficacy	
 
• Quantity (and change from baseline) of SARS-CoV-2 virus at Days 8, 14, 21 and 28
 

To assess viral sequence	
 
• Phylogenetic relationships of SARS-CoV-2 viruses sequenced from positive nasal swab samples
 

\*Baseline refers to health status prior to contracting COVID-19.

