### **9.5.3. Serious Adverse Event Definition**

An SAE is defined as any untoward medical occurrence that at any dose:

- Results in death
- Is life-threatening
- Requires in-patient hospitalization or prolongation of existing hospitalization
- Results in persistent or significant disability/incapacity
- Is an important medical event that may not be immediately life-threatening or result in death or hospitalization but may jeopardize the participant or may require intervention to prevent one of the other outcomes listed in the definition above.

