6 STUDY DESIGN CONSIDERATIONS

6.1 Study Design

This is an adaptive, randomized platform trial for treatment of early and mildly symptomatic individuals in out-patient settings with SARS-CoV-2 infection. The protocol will enroll people at high risk for COVID-19 progression based on age, BMI and comorbidity. The primary outcome through 28 days after the first intervention dose is focused on safety and efficacy (time to disease resolution or progression of disease).

Primary purpose: To assess the safety and clinical efficacy of a rivaroxaban with a primary endpoint of reduction in proportion of participants who progress to moderate or severe disease category or higher (Gates MRI ordinal scale ≥ 3) through Day 28.

Interventional model: Participants will be randomized 1:1 to either the rivaroxaban or the placebo group, in parallel for the duration of the study. Randomization will be stratified by site and by number of days since onset of symptoms at time of randomization.

Intervention groups:

Study intervention group: rivaroxaban, 10 mg (1 tablet) orally daily for 21 days.

Control group: placebo-equivalent (multi-vitamin supplement) 1 tablet orally daily for 21 days

Masking: Every effort will be made to mask the assigned treatment groups. Participants and study staff evaluating them will not be told of the assigned treatment groups. The laboratories performing the SARS-CoV-2 diagnostic testing will be blinded. Sponsor will be blinded throughout the study conduct.

Study visits: Every effort will be made to conduct the study protocol visits virtually with the study participants. A web-based video conferencing tool will be employed to allow for virtual (remote) interactions to take place between the study staff and the participant, for screening and all study visits.

Safety and efficacy monitoring: An Independent Data Monitoring Committee (IDMC) will be convened for this study for safety and efficacy monitoring with expertise in COVID-19 or respiratory viruses and emerging epidemics as well as biostatistics.

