9 OVERALL STATISTICAL CONSIDERATIONS

9.1 Determination of Sample Size

9.1.1 Efficacy

The total number of participants planned to be enrolled is approximately 600 (300 per group). If the true control rate for progression to moderate or severe category or greater is at least 30%, 294 participants per group will result in 80% power when the true study intervention effect is 35% as a relative decrease of rate progression, i.e., a true rivaroxaban rate of progression of 19.5% is 35% lower than that of a true placebo-control rate of progression of 30%. This sample size accounts for a drop-out rate of 10% and a 1-sided Type I error rate of 2.5%. To account for one planned interim futility analysis without adversely affecting the statistical power, the sample size was increased to 300 per group.

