11.1 Primary Analysis

11.1.1 Estimand

The treatment policy estimand with respect to the primary efficacy objective is defined by the following:

Population: Participants in the ITT population.

Patient-level outcome: Binary outcome of progression to moderate or severe disease category or higher (Gates MRI ordinal scale ≥ 3) at any day through Day 28.

Intercurrent events: The following intercurrent events to be taken into account:

1. If a death occurs on or prior to Day 28, the participant will be considered as having progression to moderate or severe category (Gates MRI ordinal scale ≥ 3) through Day 28.
2. If hospitalization occurs on or prior to Day 28, the participant will be considered as having progression to moderate or severe category (Gates MRI ordinal scale ≥ 3) through Day 28.
3. If a participant is lost to follow-up on or prior to Day 28, the last observed Gates MRI ordinal scale status evaluation will be carried forward onward to Day 28.
4. If a participant discontinues the study prior to initiation of IP dosing on Day 1 (for any reason: lost to follow-up, progression to moderate or severe COVID-19, withdrawal of consent) and no Gates MRI ordinal scale assessment is available, the participant will be considered as having progression to moderate or severe category (Gates MRI ordinal scale ≥ 3) through Day 28.

Participants who discontinue study intervention will be followed at least until end of study, Day 35.

Population-level summary measure: Proportion of participants who progress to moderate or severe disease category or higher (Gates MRI ordinal scale ≥ 3) at any day through Day 28.

The primary efficacy analysis will be conducted in the ITT population. Participants randomized to rivaroxaban will be compared to participants randomized to placebo. For the primary efficacy analysis, the following primary hypothesis will be tested: Prophylactic treatment with rivaroxaban will reduce progression to moderate or severe disease category or greater (Gates MRI ordinal scale ≥ 3) relative to placebo in high risk participants with mild COVID-19.

The proportion of participants who have progression of COVID-19 at any time up to and including Day 28 and the corresponding 2-sided 95% CI, computed using the Mid-p method, will be summarized for the study intervention and control. The absolute difference in the risk of progression of COVID-19 and the corresponding 2-sided 95% CI will be assessed using the

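### The headline SAE and Grade 3/4 rows mix COVID-19 worsening with other harm, and no split or between-arm difference is planned

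*SAP*

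**What the plan says.** The primary safety endpoints in Protocol Table 3 are "Frequencies of grade 3 AEs and grade 4 AEs", AEs leading to discontinuation of study intervention, and all SAEs. Protocol 9.5.1 defines an AE broadly and includes the worsening of existing conditions. Protocol 9.5.3 makes an event serious if, among other criteria, it "Requires in-patient hospitalization or prolongation of existing hospitalization", and death and life-threatening events also qualify. Neither section excludes the disease under study. Protocol 9.5 requires every SAE and every Grade 3 or 4 AE to be recorded.

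SAP 11.1.1 treats the same admissions as efficacy events: "If hospitalization occurs on or prior to Day 28, the participant will be considered as having progression". Death by Day 28 is handled in the same way.

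For reporting, SAP 12.1 plans "An AE overview table containing the frequency and percent of participants in each of the following categories", by arm, with a single-proportion mid-p 95% CI. The categories include related AEs and AESIs (major bleeding and severe hypersensitivity) as well as SAEs and Grade 3 and Grade 4 AEs. The same categories are also shown by SOC and PT. No summary leaves out COVID-19 events, and no between-arm difference is planned for any safety row.

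**The concern.** The primary safety question is how much harm rivaroxaban adds. The rows that carry the primary safety endpoints count COVID-19 admissions, deaths and severe respiratory events together with everything else. The plan expects 30% of controls to progress, and Protocol 3.2.2.1 describes progression as likely to need hospital care. Disease events could therefore be a sizeable part of these rows.

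The effect depends on what the drug does to progression:

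- **No effect on progression:** disease events add equal noise to both arms, and a drug-related excess is harder to see.
- **More progression on rivaroxaban:** the SAE row shows an excess that a reader may take for toxicity unrelated to COVID-19.
- **Less progression on rivaroxaban:** fewer disease events offset a drug-related excess, and the sign of the difference can change.

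In each case the reader needs the same thing, a rate with and without the disease events, and the plan does not supply it.

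**Working it through.** **The plan's own safety figure.** SAP 9.1.2 gives an 80% chance of at least one related SAE with 300 on rivaroxaban at a true rate of 0.54%. Check: 1 − (1 − 0.0054)^300 = 0.803. The figure reproduces. It concerns related SAEs in one arm and says nothing about the all-cause comparison.

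**Illustration 1: dilution of the SAE row.** The assumed inputs, which are not in the documents, are non-COVID SAEs of h = 3.0% on rivaroxaban and 0.5% on placebo, and a COVID-19 admission rate q independent of these. The 300 per arm is the planned size. The all-cause rate is 1 − (1 − q)(1 − h). Power is Φ(difference/SE − 1.96), two-sided 5%.

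| q, both arms | Rivaroxaban | Placebo | Difference | SE | Power |
|---|---|---|---|---|---|
| 0% | 3.00% | 0.50% | 2.50 points | 1.066 | 65% |
| 5% | 7.85% | 5.48% | 2.38 points | 2.034 | 21% |
| 8% | 10.76% | 8.46% | 2.30 points | 2.405 | 16% |

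The expected difference hardly moves; the loss comes from the larger standard error. If the drug cuts admissions by the design's 35%, from 8% to 5.2%, the rivaroxaban rate is 1 − 0.948 × 0.97 = 8.04% against 8.46% on placebo. The difference is then −0.4 points.

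**Illustration 2: harm rates taken from the protocol.** Protocol Table 2 gives 0.7% major bleeding and 2.9% clinically relevant non-major bleeding on rivaroxaban in the cited study of hospitalized patients. Assume these apply here, with zero on placebo, and that a share f of progressions qualifies as a safety event. The calculation is exact binomial with 300 per arm and a one-sided 2.5% test.

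- With disease events removed, power is about 97% for a 2.9% harm and 16% for a 0.7% harm.
- With 30% progression in both arms, power for the 2.9% harm is 39%, 21%, 13% and 8% at f = 10%, 25%, 50% and 100%.
- At the design effect (30% against 19.5%, SAP 9.1.1), the expected sign reverses once f exceeds h/(0.30 − 0.195(1 − h)). That is 0.007/0.1064 = 6.6% for a 0.7% harm and 0.029/0.1107 = 26% for a 2.9% harm.

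**Direction after the interim.** SAP section 4 records that the futility boundary was crossed. The example boundary in SAP Table 7 is p = 0.7550, or z = −0.69. With 100 per arm and pooled progression of 15% to 30%, that is an observed excess on rivaroxaban of 0.69 × √(2p(1 − p)/100) = 3.5 to 4.5 points. If, say, f = 25% of those extra progressions qualified, disease alone would add about 0.9 to 1.1 points (0.25 × 3.5 to 0.25 × 4.5) to the rivaroxaban safety row. The actual boundary and interim result are not in the documents.

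**The case against.** The strongest reply is that the plan already offers cleaner views. Major bleeding, the main harm the protocol names, is in the AESI row, which COVID-19 admissions cannot dilute. Related AEs have their own row with a CI. Every category is also broken down by SOC and PT, with each participant counted once per level, and all AEs are listed. This stands: an excess can be obscured in the headline rows without being hidden from the safety analysis as a whole.

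These views do not fill the gap completely. Participants cannot be added across terms or classes to give a non-COVID rate. The related-AE row rests on investigator judgement, and Protocol 6.7 accepts that staff may see tablets that are not identical. Clinically relevant non-major bleeding is not an AESI and has no row of its own in SAP 12.1.

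It is also fair that no between-arm safety test is planned and that the stated aim is to characterize safety. The power figures therefore measure how readable the comparison is; they are not an operating characteristic of the plan.

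A reader might infer that every progression is an SAE or a Grade 3/4 AE. The documents do not say so. Scale 3 in Protocol Table 7 needs only symptoms with shortness of breath, a respiratory rate of 20 or more, or saturation below 94%, and AE grades come from a separate table (Protocol 9.5.4). A reader might also call the overlap double counting. Efficacy and safety are analyzed separately and never summed, so counting an admission in both is not an error in itself.

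**Conclusion.** The point holds for the headline rows. COVID-19 worsening that meets an SAE or Grade 3/4 criterion enters them without exemption, and the plan has neither a participant-level rate without such events nor a between-arm safety difference. Without an efficacy effect the consequence is dilution; with worse progression on rivaroxaban it is inflated apparent harm.

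A reader might infer that the plan would mask or reverse real drug harm. Reversal needs a true benefit, which is the least likely case for SAP Version 2.0, written after the futility boundary was crossed.

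The size cannot be fixed from the documents, because the qualifying share is not stated. The fall from 65% to 21% rests on the assumed rates of 3.0%, 0.5% and 5%, on independence, and on 300 per arm, which early stopping makes optimistic. The bleeding rates in the second illustration come from hospitalized patients and may not carry over to outpatients treated for 21 days; non-major bleeds also need not reach Grade 3 or be serious. For a harm as rare as 0.7%, separating the events would not give the trial useful power. This is a worthwhile and inexpensive improvement in reporting, and it does not put the planned safety tables in error.

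**What to change.** In SAP 12.1, keep the all-cause rows as they are. Add SAE, Grade 3 and Grade 4 rows that exclude COVID-19 and its respiratory progression. Define the exclusion by a preferred-term list fixed by masked staff before unblinding. State that the list never removes bleeding events, including hemoptysis (a listed bleeding example in Protocol 6.4.1.2), or thromboembolic events. Report both versions with the between-arm risk difference and its Miettinen-Nurminen 95% CI, the method SAP 11.1.1 already specifies for efficacy.

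No new data are needed. SAP 11.4 describes a sponsor blinded throughout and SAP 7.1 places the final analysis after database lock, so the list could be fixed in time. The cost is a few extra table rows and a term list that involves judgement, which is why the all-cause rows should stay beside the new ones.

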## 2. Study Schedule of Procedures

**Table 1: Schedule of Activities**

Visits	Screening (≤5 days of Day 1)	Day 1	Day 4	Day 6	Day 8	Day 10	Day 12	Day 14	Day 18	Day 21	Day 24	Day 28	Day 35
Obtain consent	X												
Demographics, past and current medical history including known pregnancy/lactation status, and medication history	X												
Lab-confirmed SARS-CoV-2 positive diagnostic testing 	X												
Inclusion and exclusion criteria	X												
Concomitant medications	X	X	X	X	X	X	X	X	X	X	X	X	X
Randomization 	X												
Study intervention dose (Day 1 Day 21) and record adherence to dosing		X	X	X	X	X	X	X	X	X			
Clinical status assessment using ordinal scales for Gates MRI and WHO		X	X	X	X	X	X	X	X	X	X	X	X
COVID-19 signs and symptoms, temperature, oxygen saturation		X	X	X	X	X	X	X	X	X	X	X	X
AEs assessment	X	X	X	X	X	X	X	X	X	X	X	X	X
Bleeding events and severity assessment		X	X	X	X	X	X	X	X	X	X	X	X
Self-collection of nasal or oropharynx SARS-CoV-2 sample for diagnostic testing 	(X) 	X	X		X			X		X		X	

Note that visits will preferably take place remotely (refer to [Section 8](#)).

SARS-CoV-2= Severe acute respiratory syndrome coronavirus 2

Gates MRI= Bill & Melinda Gates Medical Research Institute

WHO = World Health Organization

 If there is documented positive SARS-CoV-2 diagnostic testing performed with a sample collected ≤10 days prior to screening, the test does not need to be performed. If no documentation, the potential participant will be asked to collect a nasal or oropharynx swab sample to send for testing.

 If documentation of a previous positive SARS-CoV-2 test is not available and a test is performed at screening, randomization will occur after a positive result is obtained.

 Participant will be asked to collect a sample per kit instructions. Discontinue collection during hospitalization and/or per physician's discretion when two consecutive negative results are available at any time during the study.

Note that an unscheduled visit may be required. Additional collection of a nasal swab sample may be performed based on the clinical judgement of the PI.

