## **6.4. Dose Modification and Toxicity Management**

There will be no dose modification.

Participants who experience major bleeding or clinically relevant non-major bleeding will have the study intervention discontinued (see [Section 7.1](#)) and managed according to standard of care.

Participants who experience other AEs due to the study medication may discontinue the study medication per the clinical judgment of the investigator.

At each visit, the participant will be asked if any bleeding events have occurred. Major bleeding events will be recorded as AESIs and non-major bleeding events will be recorded as AEs, in the eCRF. The following definitions will apply.

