## **9.2. Procedures at Visits from Day 4 through Day 28**

At each of these visits on Days 4, 6, 8, 10, 12, 14, 18, 21, 24, 28, the study staff conducting the visit will:

- Introduce themselves, explain their role to the participant, and confirm the identity of the participant
- Confirm that the means of contact is adequate to conduct the contact/visit
- Collect information on COVID-19 symptoms and signs
- Assess the Gates MRI and WHO ordinal scales
- Collect information on AEs
- Collect information on bleeding events and severity
- Collect information on concomitant medications
- Remind the participant to take the dose daily through Day 21, and not to show the study IP tablets or describe the tablets detailed appearance, to maintain the masking of the study staff.
- Collect information on adherence to study IP and any dosing error (if applicable)
- Ask participant to collect temperature, and oxygen saturation during the encounter (study staff will document temperature and oxygen saturation)
- Ask participant to collect nasal sample during the encounter for Days 4, 8, 14, 21 and 28
- Inquire about pregnancy, as appropriate.

As needed, additional contact with the study clinician or staff will be conducted at the request of the participant (e.g., if developing concerning symptoms or an AE).

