### **9.5. Safety Assessments**

Safety will be assessed at study encounters by the study investigator or designee. Note that unscheduled visits may be required.

Participants will be interviewed by study staff for AEs.

AEs will be collected from the time informed consent is obtained through Day 35 (14 days after the last dose of IP).

SAEs and AESIs (major bleeding and severe hypersensitivity to rivaroxaban) will be reported to the Sponsor or designee immediately (within less than 24 hours), as also any follow-up information.

All AEs must be recorded on the eCRFs if any of the following criteria have been met:

- AEs meeting SAE definition
- AEs leading to discontinuation of study intervention
- Grade 3 and grade 4 AEs
- Adverse events of special interest (AESI) including major bleeding (refer to [Section 6.4.1](#)) and severe hypersensitivity to rivaroxaban.

AEs will be assessed at the time of the collection by the investigator as related or not related to the study.

The Sponsor will be responsible for the expectedness assessment according to the available reference safety information and for complying to applicable expedited and periodic AE reporting obligations to regulatory authorities, investigators and other entities.

All AEs will be followed until resolution, stabilization, lost to follow-up, or until the end of the study (Day 35).

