6.3 Safety Measures

Safety measures include AEs assessment, bleeding events and severity assessment.

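### Bleeding is collected by severity class through Day 35, but the SAP plans no summary by class and no between-arm estimate for any bleeding category

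*SAP*

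**What the plan says.** **Collection.** Protocol Table 1, repeated in SAP Appendix 1, has a row "Bleeding events and severity assessment" marked from Day 1 to Day 35. Protocol 9.2 tells staff at each visit from Day 4 to Day 28 to "Collect information on bleeding events and severity", and 9.3 repeats this at Day 35. Protocol 6.4.1 defines three classes: major, CRNM and minimal. SAP 6.3 states: "Safety measures include AEs assessment, bleeding events and severity assessment".

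**Recording.** Protocol 6.4: "Major bleeding events will be recorded as AESIs and non-major bleeding events will be recorded as AEs, in the eCRF". The same section adds: "Participants who experience major bleeding or clinically relevant non-major bleeding will have the study intervention discontinued". Protocol 9.5 has a general rule, "All AEs must be recorded on the eCRFs if any of the following criteria have been met". Its list is serious events, events that end study treatment, grade 3–4 events and events of special interest (AESIs).

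**Reporting.** SAP 12.1 plans an overview table by arm, with a mid-p interval for each single proportion. One row is "AESIs (including major bleeding and severe hypersensitivity to rivaroxaban". All events, related events, discontinuation events, AESIs and other categories are also tabulated by system organ class and preferred term. No row or table is defined for CRNM bleeding, for major and CRNM combined, or for any bleeding. No adverse event category has a difference, ratio or test between arms.

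**The concern.** Characterizing safety is a primary objective, and Protocol 3.2 names bleeding as the drug's known risk. A reader of the final report will ask how many more participants bled on rivaroxaban than on placebo, and how seriously. The planned tables do not answer that directly. Major bleeding is expected to be too rare to compare on its own, and the commoner CRNM class has no row, total or interval. The benefit-risk statement would rest on counts that readers must piece together from many terms.

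**Working it through.** **The plan's own safety figure.** Protocol 10.1 and SAP 9.1.2 give an 80% chance of seeing at least one related serious event among 300 participants at a true rate of 0.54%. Check: 1 − (1 − 0.0054)^300 = 0.803. It reproduces, but it concerns seeing a single serious event, not bleeding by class.

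**Inputs.** Protocol Table 2 (hospital thromboprophylaxis trial, rivaroxaban 10 mg, on treatment plus 2 days): N = 3218, major 22, CRNM 93. Protocol 3.2 gives 35 ± 4 days of treatment in that trial; this trial plans 21 days. Planned rivaroxaban arm: 300.

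**Expected counts in 300 participants.**
- Major: 300 × 22/3218 = 2.05.
- CRNM: 300 × 93/3218 = 8.67.
- If risk is proportional to time (an assumption), multiply by 21/35 = 0.6: 1.2 major and 5.2 CRNM.

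**Share of clinically relevant bleeds outside the AESI row.** The table does not say how many patients had both kinds.
- No overlap: 93/(22 + 93) = 80.9%.
- Every patient with a major bleed also had a CRNM bleed: (93 − 22)/93 = 76.3%.

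The share is therefore about 76–81%. Scaling both counts by time leaves it unchanged.

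**Can class be rebuilt from the planned tables?**
- *Preferred-term tables.* Protocol 6.4.1.2 defines CRNM bleeding by clinical response, duration or extent, not by term. A short nosebleed and one that counts as CRNM can carry the same term. A participant is counted once per term, so adding terms can count one person twice, and the sum has no interval.
- *Discontinuation row.* On-treatment CRNM bleeds should enter it, but with every other event that ends treatment. A bleed after the last dose cannot enter it. That covers Days 22–35 for completers, and any time after 4 February 2021 for participants whose dosing was stopped under SAP Section 4 and who were still followed for bleeding to Day 35.
- *AESI row.* This pools major bleeding with severe hypersensitivity. The AESI table by term will normally separate them, but covers no CRNM bleeds.

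**What a class table would show.** The documents give no placebo bleeding rate, so 1, 3 and 5 events in 300 are assumed for the placebo arm. Differences are in percentage points, with unstratified Miettinen-Nurminen 95% intervals. The 11 in the composite is 2 + 9, assuming no overlap.

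| Category | Rivaroxaban | Placebo (assumed) | Difference (95% CI) |
|---|---|---|---|
| Major | 2/300 | 0/300 | 0.67 (−0.60 to 2.40) |
| CRNM | 9/300 | 1/300 | 2.67 (0.78 to 5.31) |
| CRNM | 9/300 | 3/300 | 2.00 (−0.28 to 4.73) |
| CRNM | 9/300 | 5/300 | 1.33 (−1.23 to 4.14) |
| Major or CRNM | 11/300 | 1/300 | 3.33 (1.34 to 6.15) |
| Major or CRNM | 11/300 | 3/300 | 2.67 (0.29 to 5.57) |
| Major or CRNM | 11/300 | 5/300 | 2.00 (−0.65 to 4.98) |

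Major bleeding alone says little. The composite can be informative if placebo bleeding is low, even though its intervals are wide.

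**The case against.** The strongest reply is that these bleeds are not lost. Non-major bleeds are recorded as adverse events and appear by arm in the preferred-term tables. On-treatment CRNM bleeding requires stopping study drug, and events that end treatment are a primary safety endpoint with an overview row, an interval, a term table and subgroup summaries. The Table 2 counts are on treatment plus 2 days, so the projected 8.7 bleeds belong almost entirely to that route and say nothing about bleeds after Day 21. Protocol 10.5.2 is descriptive for all safety data, so a risk difference for bleeding goes beyond what the protocol promised. The projection also uses hospitalized patients treated for longer, and a full arm of 300 that the early stop makes unlikely.

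Most of this stands, and it rules out three readings that might tempt a reader.
- *That CRNM bleeds go unreported, or that the trial could say nothing about bleeding.* They are tabulated by term and arm, and all events are listed.
- *That they alone lack a between-arm comparison.* No adverse event category has one.
- *That Protocol 6.4 and 9.5 flatly contradict each other.* Section 9.5 says what must be recorded, which can be read as a minimum, and 6.4 is the specific rule for bleeds. Only low-grade bleeds that do not end treatment are left unclear. Uneven capture across sites would be inference.

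What the reply does not answer is class. Presence in a term table or a mixed discontinuation row does not give the number of participants with a clinically relevant bleed in each arm.

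**Conclusion.** The point holds as a reporting gap of moderate weight. The plan collects severity and names it as a safety measure, then plans no output that uses the classes. At the cited rates, about 76–81% of clinically relevant bleeds fall outside the only named bleeding category: about 8.7 CRNM against 2.1 major in 300 participants, or 5.2 against 1.2 under proportional scaling. The counts assume that the Table 2 rates carry over to outpatients and that the arm is full. Actual counts may be lower, which strengthens the case for a composite rather than single terms. The share does not depend on arm size, but it does assume a similar mix of major and CRNM bleeds.

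Two limits on scope. Bleeding is not itself listed among the primary safety endpoints, so no primary endpoint is left unanalysed. Collection from Day 1 rests on the schedule and Protocol 6.5; the Day 1 procedure list in 9.1 has no bleeding item, and screening has none.

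**What to change.** Before database lock, add one table to SAP Section 12, by arm in the safety population. Give the number and percentage of participants with major, CRNM, major-or-CRNM and any recorded bleeding, each counted once per participant, on treatment and through Day 35. Add the risk difference with a Miettinen-Nurminen 95% CI, a method already in SAP 11.1.1, and label the table descriptive. Define the on-treatment window and state whether the interval is stratified.

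State that the table counts all bleeds recorded under Protocol 6.4. Note that 6.4 and 9.5 should be reconciled on the recording of low-grade bleeds that do not lead to discontinuation. With dosing already stopped, editing 9.5 would repair little; saying which bleeds were counted matters more.

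The cost is one extra table, assuming that the severity class assessed at visits is in the database. The intervals will be wide because events are few.
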